6.2 PREPARATION/HANDLING/STORAGE/ACCOUNTABILITY

6.2.1 ACQUISITION AND ACCOUNTABILITY

BIO 300 Oral Powder will be supplied to the investigational site pharmacy in foil sachets, each containing 500 mg of genistein. Sachets will be bulk packed in cardboard boxes and will be labeled as a new drug for investigational use only. All dosing cohorts will be administered whole sachets for dosing (e.g., 1 sachet for the 500 mg cohort).

Study drug used during the trial will be on an ICH compliant stability study with appropriate retest intervals. Any expired or out-of-spec drug product will be quarantined by the pharmacy and will be disposed upon full drug accountability monitoring and instruction by the Sponsor.

6.2.2 FORMULATION, APPEARANCE, PACKAGING, AND LABELING

Description and Composition

The drug product, BIO 300 Oral Powder, is an amorphous solid dispersion (ASD) [REDACTED]

[REDACTED] The composition of BIO 300 Oral Powder is shown in **Table 6.2.2.1**.

Table 6.2.2.1 BIO 300 Oral Powder quantitative composition

Component	Function	Reference to Quality Standard	Amount (mg/g)
[REDACTED]	[REDACTED]	[REDACTED]	[REDACTED]

Genistein (Bonistein®)	Active Ingredient (API)	In-house	████████
Polyvinylpyrrolidone K12	Carrier/Stabilizer	USP	████████
Sucralose	Sweetener	NF	████████

The ASD/sucralose mixture is filled into 1.5" x 2.5" high barrier, multi-layer low-density polyethylene (LDPE)/foil, individual dosing sachets. The drug product contact surface of the sachet is comprised of linear low-density polyethylene (LLDPE). ██████████

The drug product is labelled for investigational use only.

6.2.3 PRODUCT STORAGE AND STABILITY

BIO 300 Oral Powder is to be stored at 15-30°C, at ambient relative humidity by the study site pharmacy. The sachets should be stored in their original packaging until dispensed. Protection from light is not required. The sachets will be stored at the study facility and will be dispensed according to the study protocol. An extra supply of the BIO 300 Oral Powder study drug will be available in the event additional sachets are needed once the study is underway.

6.2.4 PREPARATION

The steps for preparing and dispensing BIO 300 Oral Powder are as follows:

- 1) Prepare the subject identifier label to each sachet.
- 2) Holding the sachet from the top (end with V grooves), gently swing back and forth to force all powder to the bottom of sachet.
- 3) Tear the top off the sachet being careful not to spill any powder.
- 4) Pour entire contents of sachet into mouth.
- 5) Immediately consume up to 8 oz. of water.
- 6) Inspect sachet to ensure all powder was dispensed. If not, take any residual powder immediately.
- 7) Follow steps 3 and 4 if more than 1 sachet is required. You may space the time between sachets but consume all within a 5 minute period.

6.3 MEASURES TO MINIMIZE BIAS: RANDOMIZATION AND BLINDING

This is an open label, non-randomized phase 1 trial.

6.4 STUDY INTERVENTION COMPLIANCE

Adherence to the protocol will be assessed by documenting study visits. Study intervention compliance will be assessed by accounting for the number of returned empty sachets.

6.5 CONCOMITANT THERAPY

For this protocol, a prescription medication is defined as a medication that can be prescribed only by a properly authorized/licensed clinician. Medications to be reported in the Case Report Form (CRF) are concomitant prescription medications, over-the-counter medications, and supplements.

6.5.1 PERMITTED SUPPORTIVE THERAPY

All supportive therapy for optimal medical care will be given during the study period at the discretion of the subject's attending physician(s) within the parameters of the protocol and documented on the site's source documents as concomitant medication.

6.5.2 NON-PERMITTED SUPPORTIVE THERAPY

Though no data have shown that any concomitant medications will interfere with BIO 300 Oral Powder, it is advisable that subjects do not take any other medication(s) 1 hour before or after a dose of BIO 300 Oral Powder. Concomitant medications will be collected for all subjects from the screening visit through the end of the study.

The following drugs are not permitted during the study protocol:

Anti-pulmonary fibrosis therapeutics, (e.g., imatinib, nintedanib, pirfenidone, penicillamine, colchicine, and tumor necrosis factor alpha blocker), anti-cytokine release syndrome therapeutics (e.g., anakinra, sarilumab, siltuximab, tocilizumab and/or lenzilumab), biologics used to treat asthma (e.g., omalizumab, mepolizumab, reslizumab, benralizumab and dupilumab), and all systemic corticosteroids.

If a subject receives any of the listed non-permitted supportive therapies, this will constitute as a major protocol deviation.

7 STUDY INTERVENTION DISCONTINUATION AND PARTICIPANT DISCONTINUATION/WITHDRAWAL

7.1 STOPPING CRITERIA FOR DISCONTINUATION OF THE STUDY INTERVENTION

Discontinuation of a subject and early stopping of the study intervention will be based on the following unacceptable adverse events (AEs) and must be attributable to the investigational drug BIO 300 Oral Powder (i.e., possibly, probably or definitely related to the study drug) to constitute a Dose-Limiting Toxicity (DLT).

- Non-hematologic toxicities of Grade 3 or higher, with the following exceptions:
 - anorexia
 - fatigue
 - infection without neutropenia

- Grade 3 AST/ALT elevations ≤ 7 days
- Grade 3 or 4 electrolyte abnormalities that are corrected to Grade 2 or less in less than 48 hours.
- Occurrence of a VTE (DVT or pulmonary embolism).

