1.2 SCHEMA

1.3 SCHEDULE OF ACTIVITIES (SOA)

Schedule of Events and Assessments														
Visit Number	Single Ascending Dose Cohorts					Multiple Single Dose Cohort								
	1	2	3	4	5	1	2	3	4	5-6	7	8	9	10
Day	-28 to -8	1	2	3	8	-28 to -8	1	2	3	4-5	6	7	8	13
Informed Consent	X					X								
Medical History	X					X								
Concomitant Medication	X	X	X	X	X	X	X	X	X	X	X	X	X	X
Contraception Check	X	X	X	X	X	X	X	X	X	X	X	X	X	X
Vital Signs ¹	X	X ⁸	X	X	X	X	X ¹⁷	X	X	X	X ⁸	X	X	X
Calculation of BMI	X					X								
Physical Exam ²	X			X	X	X			X		X			X
Drug Screen/Alcohol Testing	X	X				X	X							
Pregnancy test ³	X	X				X	X	X						X
Hepatitis and HIV testing	X					X								
CBC with differential ⁴	X			X	X	X			X		X			X
PT/INR, PTT	X			X	X	X			X		X			X
Serum chemistries and fasting lipid panel ⁵	X			X	X	X			X		X			X
Urinalysis ⁶	X					X	X					X		X
ECG ⁷	X	X ⁹	X	X	X	X	X ⁹	X	X		X			X
Low isoflavone dietary counseling	X	X	X	X		X	X	X	X			X		
Administer BIO 300 Oral Powder		X					X	X	X		X	X		
PK		X ¹⁰	X ¹¹	X ¹²			X ¹³				X ¹⁰	X ¹¹	X ¹²	
PD		X ¹⁴	X ¹⁵				X ¹⁴				X ¹⁶	X ¹⁵		
Adverse Event Monitoring		X	X	X	X		X	X	X	X	X	X	X	X

Notes

1. Vital signs include height, weight, BMI, resting pulse, blood pressure, respiratory rate, and temperature. Subjects should be rested semi-recumbent for at least 5 min prior to collection.
2. Physical exams will assess the HEENT, lymphatic, cardiovascular, pulmonary, gastrointestinal, musculoskeletal, and neurological systems, and anything else deemed necessary by the Investigator.
3. Pregnancy test may be performed on urine or serum
4. CBC to include white blood cell count with differential, platelet count, red blood cell count, hemoglobin, and hematocrit
5. Serum chemistries to include total protein, albumin, sodium, potassium, chloride, bicarbonate, glucose, BUN, creatinine, alkaline phosphatase, ALT, AST, uric acid, LDH, total and direct bilirubin, phosphorous, calcium, magnesium, amylase, lipase, total cholesterol, triglycerides, HDL. Subjects should fast at least 8 h prior to collection and blood will be drawn prior to test article administration.
6. Urinalysis to include pH, specific gravity, dipstick determinations of protein, glucose, ketones, blood and bilirubin and reflex microscopic exam (reflex only if any qualitative measurements or appearance return abnormal)
7. ECGs to be performed in triplicate with 5-minute intervals. Subjects should be rested supine for at least 5 minutes prior to collection.

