6.1.2 DOSING AND ADMINISTRATION

Single Ascending Dose Cohorts:

Cohort 1 dose: one BIO 300 Oral Powder sachet, 500 mg genistein

Cohort 2 dose: two BIO 300 Oral Powder sachets, 1000 mg genistein (2X the dose of Cohort 1 in the absence of dose-limiting toxicity [DLT])

Cohort 3 dose: four BIO 300 Oral Powder sachets, 2000 mg genistein (2X the dose of Cohort 2 in the absence of DLT)

Cohort 4 dose: TBD based on the observed PK and AE profiles in the first 3 dose cohorts

All single dose cohorts will be administered the drug at the clinic under the supervision of the study personnel. Subjects will follow a diet low in soy isoflavones for 7 days before and 7 days after treatment and will fast at least 8 h before dosing. Subjects will remain fasted for 4 hours after the test article

administration. Subjects will remain in the clinic 12 hours after dosing. Subjects will be provided a standardized low soy meal after the 4-hour blood draw and after the 8-hour blood draw. The purpose of fasting is to standardize the effect of food on PK and PD markers.

Multiple Single Dose Cohort:

The cohort 5 dose will be dosed daily for 6 consecutive days at the highest dose or the maximum tolerated dose from the Single Ascending Dose cohorts. Subjects will consume the test article each day within +/- 2 hours of time when the first dose was administered and not within 1 hour before or after eating. The Day 6 dose will be administered during clinic visit 7 so that PK and PD blood draws can be timed after the dose.

Drinking of room temperature water only, (up to 240 mL) will be encouraged following administration of each BIO 300 Oral Powder sachet.

Subjects will follow a diet low in soy isoflavones for 7 days before treatment, during the 6 days of treatment and 7 days after treatment. Subjects will fast at least 8 h before the first dose, 3rd dose and the 6th dose. Subjects will remain in the clinic 4 h after the first dose and 12 hours after the 6th dose. Subjects will remain fasted for 4 hours after the test article administration on days 1 and 6. On the 6th day, subjects will be provided a standardized low soy meal after the 4-hour blood draw and after the 8-hour blood draw. The purpose of fasting is to standardize the effect of food on PK and PD markers.

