7.2 DISCONTINUATION OF STUDY INTERVENTION

Discontinuation from BIO 300 Oral Powder does not mean discontinuation from the study, and the remaining study procedures should be completed as indicated by the study protocol. If a clinically significant finding is identified (including, but not limited to changes from baseline) after enrollment, the Principal Investigator or qualified designee will determine if any change in participant management is needed. Any new clinically relevant finding will be reported as an adverse event (AE).

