All subjects will have their blood collected for serum as described above. Serum samples will be collected for pharmacokinetics just prior to and following administration of a single dose of BIO 300 Oral Powder at 30 minutes, 1, 2, 4, 6, 8, and 12 hours. The time of the blood draw will be ± 10 minutes of the nominal time. Subjects will be given a standardized low-soy meal after the 4 h blood draw and 2 h after the 6 h blood draw. Whole blood will be collected as described above for RNA isolation prior to a single dose BIO 300 Oral Powder administration, and at 1, 2 and 4 hours after administration.

Visit 3 (Day 2)

All subjects will have blood serum collected for PK 24 ± 2 hrs after BIO 300 Oral Powder dosing. Whole blood will also be collected for RNA isolation 24 ± 2 hrs after BIO 300 Oral Powder dosing.

Visit 4 (Day 3)

All subjects will have a whole blood and serum collected for CBC, PT/INR, PTT, 48 ± 4 hrs PK and serum chemistry as described above.

Visit 5 (Day 8)

All subjects will have a whole blood and serum collected for CBC, PT/INR, PTT and serum chemistry as described above.

Multiple Single Dose

Visit 1 (Screening)

At the screening visit, blood will be collected to acquire the subject's baseline blood counts, serum chemistries, PT/INR, PPT, and viral testing. If a pregnancy test is required for the subject, either a serum or urine test will be done at this time. These test results will assist in determining the subject's ability to be included in the trial (see **Section 5.1 Inclusion Criteria**).

Visit 2 (Day 1)

All subjects will have their blood collected for serum as described above. Serum samples will be collected for pharmacokinetics just prior to and following administration of a single dose of BIO 300 Oral Powder at 30 minutes, 1, 2 and 4 hours. The time of the blood draw will be ± 10 minutes of the nominal time. Whole blood will be collected as described above for RNA extraction prior to a single dose BIO 300 Oral Powder administration, and at 1, 2 and 4 hours after administration.

Visit 4 (Day 3)

All subjects will have a whole blood and serum collected for CBC, serum chemistry, and PT/INR, PPT as described above.

Visit 5 and 6 (Days 4 and 5)

All volunteers will have their vital signs performed and will be administer a single dose of BIO 300 Oral Powder at the research unit.

Visit 7 (Day 6)

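### In cohort 5 the 7-day allowance for Grade 3 AST/ALT rises outlasts dosing, so duration can never trigger the protocol 7.1 stop; and the SAP reports DLTs without choosing between two definitions

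*Combined protocol and SAP*

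**What the plan says.** **Stopping rule.** Protocol 7.1 lists the events that stop a subject's dosing and that count as a DLT. They must be at least possibly related to the drug. The core criterion is non-hematologic toxicity of Grade 3 or higher, with exceptions, and venous thromboembolism is added. Two of the exceptions concern laboratory values: "Grade 3 AST/ALT elevations ≤ 7 days" and "Grade 3 or 4 electrolyte abnormalities that are corrected to Grade 2 or less in less than 48 hours".

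**Cohort 5 schedule.** Protocol 6.1.2 states: "The cohort 5 dose will be dosed daily for 6 consecutive days". Each dose is taken "within +/- 2 hours of time when the first dose was administered". Serum chemistry after dosing starts is scheduled on Days 3, 6 and 13 (Schedule of Activities; 8.3; 8.3.2). Note 5 to the Schedule of Activities adds: "Subjects should fast at least 8 h prior to collection and blood will be drawn prior to test article administration". For the visits on Days 4 and 5, section 8.3 says: "All volunteers will have their vital signs performed and will be administer a single dose of BIO 300 Oral Powder at the research unit". No chemistry is scheduled on those days.

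**Discretion.** Under 7.2, after a clinically significant finding, "the Principal Investigator or qualified designee will determine if any change in participant management is needed". Section 7.3 lets the investigator withdraw a subject for a laboratory abnormality.

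**DLT elsewhere.** Section 7.5 gives its own DLT definition for the escalation rule: any Grade 3 or 4 event on the FDA toxicity scale for vaccine-trial volunteers. SAP 9.1 reports the proportion of subjects with DLTs in each dosing cohort. SAP 10.2 lists a DLT summary beside a summary of all Grade 3 or 4 events. Neither SAP section defines DLT or points to 7.1 or 7.5.

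**The concern.** A stopping rule should tell the site what to do on the day the result arrives. The AST/ALT exception depends on how long the rise lasts, and in cohort 5 that cannot be known until dosing is over. Section 7.1 does not say whether a rise of unknown duration stops dosing or is excepted in the meantime.

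Cohort 5 is the only part of the trial with a later dose to withhold. It is dosed at the top or maximum tolerated level from the single-dose part, in volunteers who are offered no treatment benefit (2.2.2). Raised liver enzymes are one of only two risks that 2.2.1 classes as rare but serious.

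The second matter is one of reporting. The adverse-event profile is a primary objective, and the DLT proportion per cohort is one of its summaries. A reader of the results could not tell which definition lay behind it.

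**Working it through.** The plan gives no figure of its own on this point, so the check is a clock calculation followed by a comparison of the two definitions.

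**Inputs**
- Six daily doses, each within 2 h of the first dose's clock time (6.1.2).
- AST/ALT exception of 7 days (7.1): 7 × 24 = 168 h.
- Chemistry on Days 3, 6 and 13, drawn before that day's dose (Schedule of Activities and note 5).
- Cohort sizes: 6 completers per single-dose cohort; in cohort 5, 10 recruited (5M/5F) for at least 8 completers (4M/4F) (synopsis; SAP section 4).

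**Can the allowance run out while doses remain?**
- Dose 1 to dose 6: 5 × 24 = 120 h, ± 2 h, giving 118–122 h.
- The earliest possible drug-caused rise begins at dose 1. At dose 6 it has used 118/168 = 70.2% to 122/168 = 72.6% of the allowance.
- The allowance closes 168 − 122 = 46 h to 168 − 118 = 50 h after the last dose.
- Counted from a Day 3 sample drawn just before dosing (46–50 h after dose 1), the time to dose 6 is 118 − 50 = 68 h to 122 − 46 = 76 h, or 40.5% to 45.2% of the allowance.

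So elapsed duration cannot trigger the stop before the last dose, whichever starting point is used.

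**How many doses are exposed?** For a Grade 3 value in the Day 3 sample, the number depends on result turnaround, which the protocol does not give:
- known before the Day 3 dose: doses 3 to 6, 4 of 6;
- known by Day 4: doses 4 to 6, 3 of 6;
- known by Day 5: doses 5 and 6, 2 of 6.

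The next scheduled draws come 3 days later (Day 6) and then 7 days after that (Day 13). Scheduled sampling alone therefore barely resolves a 7-day limit.

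**The two DLT definitions**

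| Feature | Protocol 7.1 | Protocol 7.5 |
|---|---|---|
| Core | Non-hematologic, Grade 3 or higher | Any Grade 3 or 4 event on the FDA scale |
| Hematologic events | Outside the core criterion | Not excluded |
| Exceptions | Five, including AST/ALT and electrolytes | None |
| Attribution to drug | Required | Only in the bullet on 4 of 8 subjects |
| Venous thromboembolism | Named | Not named |

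Take an attributable Grade 3 ALT rise that lasts 5 days. It is not a DLT under 7.1. It is one under 7.5, provided the FDA scale lists liver enzymes. Section 8.4.3.1 says the scale grades laboratory abnormalities, but the scale itself is not in the documents. One subject classified differently moves the reported proportion by 1/6 = 16.7 points in a single-dose cohort, and in cohort 5 by 1/8 = 12.5 points (8 subjects) or 1/10 = 10.0 points (10 subjects).

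**The case against.** **The line may not be an exception at all.** Its bullet level is unclear in the extracted text. As a separate stopping criterion, though, it would duplicate the Grade 3 rule and single out short rises, and the electrolyte line would make corrected abnormalities a reason to stop. Only the exception reading makes sense, but it remains an inference.

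**An open rise can be read as not yet excepted.** The default is that an attributable Grade 3 event stops dosing, and a rise might earn the exception only once it is known to have ended in time. This is a fair reading, and a cautious site may adopt it. But a site that redoses also complies with 7.1. The electrolyte exception is likewise known only in retrospect; it does at least name a result that must be seen, whereas the AST/ALT line names only a duration.

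**Safeguards exist.** Sections 7.2 and 7.3 give the investigator discretion. The Safety Monitoring Committee can recommend suspension or a regimen change (SAP section 6), and the Medical Monitor shares oversight (10.1.6). Section 8.4.7 sends significant laboratory abnormalities to the sponsor, and 8.4.4 requires follow-up to resolution. These lower the practical risk. They permit a hold but do not require one, and none sets a repeat-test interval.

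**The DLT difference is partly a labelling matter.** SAP 10.2 lists every adverse event by cohort, and relatedness and dates are recorded (9.4.4), so in cohorts this small a reader could largely recount. That stands, but the headline proportion should not need recounting.

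**Conclusion.** The concern holds in two parts.

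1. In cohort 5 the 168 h allowance exceeds the 118–122 h from first to last dose. Up to four of six doses can follow an attributable Grade 3 AST/ALT value on Day 3 without a breach of 7.1. This rests on the exception reading of the AST/ALT line and, for the exact number of doses, on result turnaround.
2. Sections 7.1 and 7.5 define DLT differently, and SAP 9.1 and 10.2 name neither.

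A reader might go further on three points, and the documents do not support it.
- **That the plan directs redosing, or leaves liver signals unguarded.** It does not: Grade 4 AST/ALT is not excepted, and discretion and oversight apply to Grade 3.
- **That dose escalation was compromised.** Section 7.5 points to its own definition for escalation, and the amendment history (10.3) indicates that all four single-dose cohorts are complete.
- **That the harm is likely.** The documents give no rate for such rises, so no probability can be attached.

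This is a cheap improvement in safety wording and reporting, not a flaw that invalidates the design.

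**What to change.** **Protocol 7.1, for cohort 5.** Delete the AST/ALT duration exception, so that an attributable Grade 3 AST/ALT value stops dosing. Alternatively, state that such a value holds the next dose until a repeat chemistry at the next daily visit shows Grade 2 or less.

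**SAP 9.1 and 10.2.** Name one DLT definition and cite its protocol section. Leave 7.5 as it stands, since it is the rule that governed the completed single-dose escalation.

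**Cost**
- The protocol change is an amendment and needs IRB approval.
- The hold option adds one or two 3.5 mL draws in an affected subject only: 3.5/146.3 = 2.4% to 7/146.3 = 4.8% of the cohort 5 blood total. Days 4 and 5 are already clinic visits. Note 5 asks for an 8 h fast before chemistry, which 6.1.2 requires only before doses 1, 3 and 6, so the repeat would need a fast or a stated waiver.
- A stopped or held subject may lose the Day 6 PK profile, which is part of a primary endpoint. With 5M/5F recruited for 4M/4F completers, one loss per sex (5 − 4 = 1) can be absorbed before a backup is needed; two losses in the same sex would call on the 2M/2F backups.

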7.2 DISCONTINUATION OF STUDY INTERVENTION

Discontinuation from BIO 300 Oral Powder does not mean discontinuation from the study, and the remaining study procedures should be completed as indicated by the study protocol. If a clinically significant finding is identified (including, but not limited to changes from baseline) after enrollment, the Principal Investigator or qualified designee will determine if any change in participant management is needed. Any new clinically relevant finding will be reported as an adverse event (AE).

7.3 PARTICIPANT DISCONTINUATION/WITHDRAWAL FROM THE STUDY

Subjects are free to withdraw from participation in the study at any time upon request. The Principal Investigator may discontinue or withdraw a subject from the study for the following reasons:

- Pregnancy (see **Section 8.4.8**). Women of childbearing potential must perform a pregnancy test in case of delayed menstruation and stop treatment immediately in case of positive result.
- Significant study intervention non-compliance.
- Any clinical adverse event (AE), laboratory abnormality, or intercurrent illness that, in the opinion of the Principal Investigator, indicates that continued participation in the study is not in the best interest of the participant.
- If the participant meets an exclusion criterion (either newly developed or not previously recognized) that precludes further study participation.
- If the participant withdraws their informed consent.

The reason for participant discontinuation or withdrawal from the study will be recorded on the Case Report Form (CRF). Subjects who sign the informed consent form and are randomized but do not receive the study intervention may be replaced.

